The authors previously reported that, when an early recovery program was applied after laparoscopic right hemicolectomy for right-sided colon cancer, the end-to-side anastomosis group had a higher cumulative recovery rate on postoperative day 7 (71.7% vs. 93.0%, $p = 0.019$), a shorter length of hospital stay (7 vs. 6 days, $p = 0.003$), and a lower complication rate (26.1% vs. 4.6%, $p = 0.008$) compared to the side-to-side anastomosis group (7). Another study reported that side-to-side anastomosis was a major factor contributing to early recovery program failure in patients, including those with not only right-sided colon cancer but also left-sided and sigmoid colon cancer (8).

2) Hypothesis and purpose

Currently, there is no established standard anastomotic technique for laparoscopic right hemicolectomy. End-to-side anastomosis is considered anatomically ideal, and it is hypothesized that it may result in superior short-term outcomes. This study aims to demonstrate the superiority of end-to-side anastomosis through a prospective randomized comparative study between end-to-side and side-to-side anastomosis.

9. Investigational Drug and Medical Device Code Name (or Generic Name of Active Ingredient), Quantity of Active Ingredient, Dosage Form (Including Comparator) : Not applicable.

10. Selection Criteria, Exclusion Criteria, Target Sample Size, and Rationale for Sample Size Calculation

1) Selection Criteria:

Subjects must meet all of the following conditions:

① Patients with right-sided colon cancer

Right-sided colon cancer is defined as tumors located from the cecum to the hepatic flexure. The histological type is limited to adenocarcinoma.

- ② Patients aged between 18 and 80 years
- ③ Patients with adequate bone marrow function:
Hemoglobin ≥ 10 g/dL (in cases of simple iron deficiency anemia, correction is required)
White blood cell count $\geq 4,000/\text{mm}^3$
Platelet count $\geq 100,000/\text{mm}^3$
- ④ Patients with adequate renal function (Creatinine ≤ 1.5 mg/dL)
- ⑤ Patients without significant functional impairment of the heart, lungs, or other major organs
- ⑥ Patients who have signed the written informed consent form

2) Exclusion Criteria

Patients who meet any of the following conditions will be excluded from this clinical trial:

- ① **Patients with distant metastasis or local invasion to the small intestine, ureter, or other adjacent structures requiring combined resection**

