- ② **Patients in whom laparoscopic surgery is not feasible due to a history of prior abdominal surgery or the severity of the disease**
- ③ **Patients requiring emergency surgery due to bowel obstruction or peritonitis**
- ④ **Patients taking other oral medications for bowel movement disorders, such as chronic constipation, before surgery**
- ⑤ **Patients with severe cardiopulmonary disease, mental illness, or other comorbidities that prevent the application of the early recovery program**
- ⑥ **Patients who do not consent to the study or do not sign the informed consent form**
- ⑦ **Patients deemed ineligible for clinical trial participation based on the physician's judgment**

3) Target Sample Size and Rationale for Sample Size Calculation

This study aims to evaluate the superiority of end-to-side anastomosis over side-to-side anastomosis in terms of short-term outcomes. The sample size was calculated based on previous studies (7,9).

Allocation ratio: 1:1

Type I error (α): 5%

Power: 80%

Expected difference in 7-day cumulative recovery rate: 20% (End-to-side: 90% vs. Side-to-side: 70%)

Expected dropout rate: 10%

The calculated sample size is as follows:

◆ Target number of participants: 130

End-to-side anastomosis group: 65 participants

Side-to-side anastomosis group: 65 participants

(The sample size will be further reviewed and adjusted upon consultation with the Clinical Research Institute at Seoul National University.)

◆ Randomization

The **allocation ratio** between groups will be **1:1**.

The anastomosis method will be determined preoperatively using a **random table or computer-generated randomization program**.

Group allocation will be revealed **in the operating room just before anastomosis**.

(The randomization process will be conducted in consultation with the Clinical Research Institute at Seoul National University.)

4) Recruitment Plan

There will be **no public recruitment announcement** for participant enrollment. Instead, patients admitted for **laparoscopic right hemicolectomy** for right-sided colon cancer will be provided with detailed information about the study, including its objectives, safety, and potential risks. After obtaining written informed consent, eligible patients will be enrolled in the study.

11. Study methods

1) Detailed methods

(1) Design

: Prospective randomized clinical trial

(2) Classification of Patient Groups

① **Patient group classification will be revealed just before surgery.**

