- ① **No issues for 24 hours after diet initiation** (at least one-third intake of liquid diet or higher).
- ② No additional analgesic administration after discontinuation of patient-controlled analgesia (PCA).
- ③ No major complications and stable afebrile condition (body temperature $\leq 37.2^{\circ}\text{C}$).
- ④ No issues with ambulation (ability to walk a distance of at least 600 meters).

(2) Secondary Endpoint

- **Length of hospital stay**
- **Complications**
- **Failure rate of the early recovery program**
- **Readmission rate within one month after surgery**

5) Criteria and Methods for Efficacy Evaluation

This study evaluates the superiority of end-to-side anastomosis over side-to-side anastomosis in terms of short-term outcomes. The sample size was calculated based on previous studies (7,9).

- **Allocation ratio:** 1:1
- **Type I error (α):** 5%
- **Power:** 80%
- **Expected difference in 7-day cumulative recovery rate:** 20% (End-to-side: 90% vs. Side-to-side: 70%)
- **Expected dropout rate:** 10%

The hypothesis to be tested is that the **cumulative recovery rate** in the end-to-side anastomosis group is 20% higher than in the side-to-side anastomosis group.

6) Differences from Existing Treatments and Studies

Both **end-to-side and side-to-side anastomosis** are standard anastomotic techniques commonly used in clinical practice, meaning that this study does not involve a new or experimental treatment. However, research specifically comparing **anastomotic techniques in right-sided colon cancer** is limited, with most existing studies being retrospective cohort studies. Thus, this study will be the first prospective, randomized controlled trial investigating anastomotic methods in right-sided colon cancer.

7) Benefits and Risks for Study Participants

Since this study compares two **existing standard anastomotic techniques**, there are minimal risks or additional benefits associated with participation. Furthermore, the scientific and medical knowledge gained from this research is expected to far outweigh any potential risks or **adverse effects** experienced by study participants.

8) Discontinuation and Withdrawal Criteria

- ① Conversion to open surgery during the procedure due to safety concerns that make continued laparoscopic surgery unsafe for the patient.
- ② Participants who initially consented to the study but later decide to withdraw their consent.

9) Criteria, Methods, and Reporting for Adverse Events and Safety Evaluation

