B. Safety review will be conducted as follows to determine study modification or termination:

- If a serious and unexpected adverse event occurs:
 - (A) The principal investigator will review the event and decide on study modification or termination.
 - (B) If the IRB review results in a decision to modify or terminate the study, the research team will comply with the IRB's directive.
- Safety review will be conducted once every 6 months:
 - (A) The principal investigator will review all adverse events that occurred in the past 6 months and determine whether study modification or termination is necessary.
 - (B) The findings reviewed in section (A) will be reported as an "Other Report" to the respective Institutional Review Board (IRB) of each institution.

11) Data Analysis and Statistical Methods

- Statistical analysis will be conducted using SPSS or STATA. A p-value of ≤ 0.05 will be considered statistically significant.
 - Continuous variables: Student's t-test, Mann-Whitney U test
 - Binary variables: χ^2 -test, Fisher's exact test
- If advanced statistical analysis techniques are required, consultation with the Medical Research Institute will be sought for expert statistical guidance and analysis.

12) Study Schedule

Contents	Duration											
	2	4	6	8	10	12	14	16	18	20	22	24
IRB Review	■											
Selection of Study Participants and Obtaining/Registration of Informed Consent		■	■	■	■	■	■	■				
Data collection			■	■	■	■	■	■				
Statistical analysis									■	■		
Final Report										■	■	
Final Research Paper										■	■	

12. Measures for the Protection of Study Participants' Safety

1) Basic Measures to Ensure Ethical Conduct of the Study

- The study will comply with the Declaration of Helsinki (2013 revision) and ICH-GCP guidelines.
- The study will be conducted only after obtaining IRB approval.

2) Informed Consent Process for Study Participants

- ① Researchers responsible for explaining the study and obtaining consent: A physician among the research team.
- ② Individuals providing consent: Study participants.
- ③ Waiting period between study explanation and consent acquisition: 20 minutes.
- ④ Methods to minimize coercion or undue influence:
 - a. The researcher (usually the attending physician) will explain the study to the participant.
 - b. The research coordinator will provide additional explanations in a separate space.
 - c. The researcher will confirm if the participant has any additional questions before obtaining consent.

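### Does calling the 20% planning difference the hypothesis to be tested leave the trial testing something it cannot show?

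*Combined protocol and SAP*

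**What the plan says.** The aim in the protocol's Hypothesis and purpose section is directional but has no number attached: of end-to-side anastomosis, "it is hypothesized that it may result in superior short-term outcomes". Section 10, 3) gives the planning inputs: 1:1 allocation, "Type I error (α): 5" percent, power 80%, dropout 10%, and "Expected difference in 7-day cumulative recovery rate: 20% (End-to-side: 90% vs. Side-to-side: 70" percent). The result is "Target number of participants: 130", 65 per arm.

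Section 11, 5) opens by saying that the study evaluates superiority and repeats those inputs. It then adds a sentence beginning "The hypothesis to be tested is that the" cumulative recovery rate "in the end-to-side anastomosis group is 20% higher than in the side-to-side anastomosis group".

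Section 11, 11), like the Statistical Analysis row of the Study Overview, lists the χ²-test and "Fisher's exact test" for binary variables. It says that a p-value of 0.05 or less "will be considered statistically significant". The documents state no null hypothesis, no sidedness, no rule for choosing between the two tests, and no confidence interval for the difference.

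**The concern.** The sentence in Section 11, 5) is the only numeric hypothesis for the primary endpoint, and it stands apart from the expected-difference line. Taken at face value, the claim to be established is a 20-point advantage, while the listed tests can establish only that the rates are not equal. A significant result would then not answer the stated hypothesis.

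The same data could be reported in two ways. Take 58/65 against 46/65, a difference of 12/65 = 18.5 points. Chi-square gives p = 0.009, yet the 95% interval (Newcombe) runs from 4.7 to 31.6 points. That is significant under Section 11, 11), but it does not demonstrate 20 points. If the protocol really held two criteria for success, the choice between them could be made after the data were seen.

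**Working it through.** **1. Reproduce 130.** Inputs are from Section 10, 3): 90%, 70%, α = 0.05, power 0.80, dropout 10%. With unpooled variance, two-sided, against a null of no difference:

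n = (1.960 + 0.842)² × (0.9×0.1 + 0.7×0.3) / 0.20² = 7.849 × 0.30 / 0.04 = 58.87, so 59 per arm.

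59 × 1.10 = 64.9, so 65 per arm and 130 in total. Dividing by 0.9 instead gives 65.6, so 66 per arm and 132. A one-sided 5% formula with continuity correction gives 57.97, so 58 per arm; 58/0.9 = 64.4, so again 65 and 130. The pooled two-sided formula without correction (62 per arm, 138 in total) does not match. Both routes to 130 have a null of no difference.

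**2. Power of the listed tests.** Exact enumeration of two binomials at 90% and 70%, two-sided p ≤ 0.05:

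| Evaluable | Pearson chi-square | Fisher |
|---|---|---|
| 117 (58/59 or 59/58) | 79.5% | 73.0% to 76.8% |
| 130 (65/65) | 83.2% | 77.5% |

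The chi-square figures agree with the planned 80%. The 117 assumes that all of the 10% dropouts leave the analysis.

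**3. The literal margin reading.** Suppose the null were a difference of 20 points or less. The mean of the test statistic is (true difference − 0.20)/SE. At 90% and 70% this is 0/SE = 0, so power equals α whatever the sample size: 2.5% or 5% one-sided. Exact Wald calculations agree: 2.5% to 2.7%, and 5.2%.

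It barely improves at the earlier study's 93.0% and 71.7%, quoted in the background. For 80% power at two-sided 5%, the number per arm would be 7.849 × (0.93×0.07 + 0.717×0.283) / 0.013² = 7.849 × 0.268 / 0.000169, about 12,450. A plan for 65 per arm cannot have meant this.

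**4. Significant, but under 20 points observed.** At a true 90% and 70%, 25.8% to 29.5% of trials with 117 evaluable patients (28.7% with 130) reach p ≤ 0.05 with an observed difference below 20 points. That is 32% to 37% of the significant trials. But 46% to 50% of all trials fall below 20 points when the truth is 20, because an estimate falls below its true value about half the time. Any trial with a planning effect shows the same pattern.

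**5. Which test.** At the planning rates the average non-recovery is (10% + 30%)/2 = 20%, so the smallest expected count is 0.20 × 58 = 11.6 with 58 per arm and 0.20 × 65 = 13 with 65. The familiar rule of using Fisher only for expected counts below 5 therefore selects chi-square. The choice can matter at the edge: 58/65 against 49/65 gives p = 0.039 by chi-square and 0.064 by Fisher. In that table the expected non-recovered count is (7 + 16)/2 = 11.5 per arm, so the rule again selects chi-square.

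**The case for a change.** The best argument for a change is that the protocol already has a line for the expected difference, and then separately gives the same 20% as the hypothesis under test, in the section that sets the efficacy criteria. A report could call a significant 15-to-19-point result either confirmation or failure and cite the protocol for both. Sidedness cannot be recovered from the sample size, since one-sided and two-sided calculations both reach 130. The choice between chi-square and Fisher is open. Clearer wording would cost two sentences and no patients.

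Part of this stands. The wording is loose, and the null, the sidedness and the choice of test are unwritten. The choice of test is worth at most 79.5 − 73.0 = 6.5 points of power at the planning rates.

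The claim of two success criteria does not stand. The sentence says that the rate is 20% higher, not that a difference of more than 20 points must be shown, so the margin null has to be supplied by the reader. The 18.5-point example does not give opposite verdicts either: its interval excludes zero and includes 20, so it supports superiority and is compatible with the planning effect. On sidedness, a chi-square p-value as ordinarily reported does not depend on direction, so applying the listed test at 0.05 gives a two-sided 5% test.

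**Conclusion.** No change is needed. The sentence is a slip of wording in which the alternative used for sizing is presented as the hypothesis. Its own section opens with superiority, the expected-difference line sits just above it, and p ≤ 0.05 is the only decision rule. An analyst who follows the plan tests equal rates with about 80% power by chi-square (79.5% to 83.2%). Rewording would leave the sample size, tests, threshold and result as they are. The 2.5% to 5% power figure belongs to a margin that the plan does not set.

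The unstated null, sidedness and test rule are missing detail that would be filled sensibly: equal rates, two-sided, and chi-square because expected counts are well above 5. Reporting the difference with an interval is ordinary practice and would keep a significant result from being read as proof of 20 points.

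This rests on reading 20% as percentage points, which the 90% and 70% beside it support, and on true rates near those planned.

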Comparison of surgical outcomes between end-to-side and side-to-side anastomosis after laparoscopic right hemicolectomy: a prospective randomized controlled trial

Version No: 1.0

Principal Investigator Affiliation: Bundang Seoul National University Hospital

Principal Investigator Name: [name]

Confidentiality: All information contained in this research protocol is provided for the principal investigator, research staff, and the Institutional Review Board. Except for obtaining written consent for research participation, this information may not be disclosed to any third party without prior written consent from Bundang Seoul National University Hospital.

Study Overview

Study Title	Comparison of surgical outcomes between end-to-side and side-to- side anastomosis after laparoscopic right hemicolectomy: a prospective randomized controlled trial
Principal Investigator	[name], Department of Surgery, Bundang Seoul National University Hospital
Funding Institution	Bundang Seoul National University Hospital (In-House Research Project: 14-2016-016)
Study Objective	There is ongoing debate regarding the relationship between anastomotic techniques and surgical outcomes (such as recovery period and complications). To date, no prospective randomized clinical study has been reported comparing postoperative outcomes between end-to-side and side-to-side anastomosis following right hemicolectomy. This study aims to establish a standard anastomotic method after right hemicolectomy.
Study Design	a single center prospective randomized controlled trial
Study Duration	IRB Approval Date – June 30, 2018
Study Subjects	Patients scheduled for laparoscopic right hemicolectomy for right-sided colon cancer at Bundang Seoul National University Hospital.
Number of Study Subjects	130 patients (65 in the end-to-side anastomosis group, 65 in the side-to-side anastomosis group).
Vulnerable Study Subjects	Not applicable.
Investigational Drug/Medical Device	Not applicable.
Dosage and Administration	Not applicable.
Study Method	After random allocation of the anastomotic technique during surgery, a comparative analysis will be conducted between the two groups on cumulative recovery rate, length of hospital stay, complications, failure rate of the early recovery program, and readmission rate within one month after surgery.

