② **Patients will be randomly assigned into two groups: the end-to-side anastomosis group and the side-to-side anastomosis group.**

③ **Except for the anastomotic method, all other procedures will be conducted identically in both groups.**

[figure not shown]

Figure 1. Schematic Diagram of Side-to-Side Anastomosis (a) and End-to-End Anastomosis (b)

(3) Postoperative Management

① **All patients participating in the study will undergo the Enhanced Recovery Program (ERP) after surgery.**

② **The ERP protocol applied will be based on the protocol used in the researchers' previous studies.**

③ **If complications such as ileus or obstruction occur during the application of the ERP, the program will be immediately discontinued, and appropriate examinations and treatments will be administered at the physician's discretion. In such cases, it will be considered a failure of the ERP application.**

Operative day	diet		exercis
Operative day	Sow of water	
 After 4 hours of arrival in the hospital room from the operating room, initiate oral intake after confirmation by the attending medical staff. Start with small sips to moisten the mouth and gradually increase the intake instead of consuming a large amount at once. However, the total dietary intake should not exceed 1 liter per day. If symptoms such as nausea, vomiting, or abdominal pain occur, discontinue oral intake and perform necessary examinations and treatments. 	
 Sit for a total of 1 hour per day. Spend at least one hour per day out of bed. Sitting can be divided into 4 sessions of 15 minutes each or 6 sessions of 10 minutes each. Various options are allowed, such as sitting on the edge of the bed or sitting on the caregiver's bed.
Postoperative Day 1	Liquid diet (three times a day)	
 Like water, liquid food should be consumed in small amounts initially and gradually increased rather than taken in large quantities at once. There is no strict limitation on the amount, but if symptoms such as nausea, vomiting, or abdominal pain occur, discontinue intake and perform necessary examinations and treatments. 	
 Sit for a total of 3 hours per day. Walk in the hospital corridor. If walking alone is difficult, assistance from a caregiver or the use of a walker is allowed.

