Postoperative Day 2	Soft porridge (three times a day)	There is no strict limitation on the amount, but if symptoms such as nausea, vomiting, or abdominal pain occur, discontinue the diet and perform necessary examinations and treatments.	Walking in the hospital corridor: Walk back and forth along the corridor at least three times. If walking alone is difficult, assistance from a caregiver or the use of a walker is allowed.
After Postoperative Day 2	Soft porridge (three times a day)	There is no strict limitation on the amount, but if symptoms such as nausea, vomiting, or abdominal pain occur, discontinue the diet and perform necessary examinations and treatments.	Walking in the hospital corridor: Walk back and forth along the corridor at least three times. If walking alone is difficult, assistance from a caregiver or the use of a walker is allowed.

Table 1. Implementation of the Early Recovery Program

(4) Data Collection Items

- ① **Basic patient data** (age, sex, body mass index, medical history, ASA grade)
- ② **Preoperative staging** (CT, endoscopic findings)
- ③ **Intraoperative findings** (operative time, intraoperative blood loss)
- ④ **Postoperative course** (gas out time, length of hospital stay, recovery time, occurrence of complications)
- ⑤ **Histopathological results and staging**
- ⑥ **Readmission within one month after surgery and its reason**

2) Control Group Setting and Randomization Method

A comparison will be made between end-to-side anastomosis and side-to-side anastomosis.

Randomization will be conducted using the **SAS program**, managed by the **MRCC at Bundang Seoul National University Hospital**. A random number will be generated, assigned a serial number, and the anastomotic method will be delivered just before surgery to ensure random allocation.

3) Investigational Drug Administration/Usage, Method of Administration, Concomitant Therapy, and Justification for Comparator Use

Not applicable.

4) Observation Items, Clinical Examination Items, and Evaluation Methods for Study Outcomes

(1) Primary Endpoint: 7-Day Cumulative Recovery Rate

The **cumulative recovery rate** is defined as the percentage of patients who have reached **recovery time** within a specific postoperative period.

The definition of **recovery time** is based on previous studies by the investigators (7, 9) and is defined as the postoperative time at which **all** of the following conditions are met:

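### Conversion to open surgery is a withdrawal criterion, nothing keeps converted patients in the 7-day recovery denominator, and the protocol gives conflicting times for revealing the arm

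*Combined protocol and SAP*

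**What the plan says.** **Conversion.** Section 11, item 8 (Discontinuation and Withdrawal Criteria) has two entries. One is withdrawn consent; the other is "Conversion to open surgery during the procedure due to safety concerns that make continued laparoscopic surgery unsafe for the patient".

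**Denominator.** Section 11, item 4(1) says the cumulative recovery rate "is defined as the percentage of patients who have reached" recovery time within a given period. It does not say which patients count. Section 11, item 11 and the Study Overview name software, a p-value threshold and tests, but no analysis set and no rule for withdrawn patients. By contrast, section 11, item 1(3) does settle a patient whose recovery program is stopped for a complication: "In such cases, it will be considered a failure of the ERP application".

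**Reveal of the arm.** Four statements bear on timing:
- Section 10, item 3 (Randomization): allocation is revealed "in the operating room just before anastomosis".
- Section 11, item 1(2): "Patient group classification will be revealed just before surgery".
- Section 11, item 2: "the anastomotic method will be delivered just before surgery to ensure random allocation".
- Study Overview, Study Method: "After random allocation of the anastomotic technique during surgery".

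**The concern.** Placed beside withdrawn consent, conversion reads as a reason to leave the study, and a patient who has left would normally drop out of a simple percentage. If the surgeon already knows the arm, the decision that removes the patient comes after randomisation and may be related to it. A chi-square or Fisher test on the remaining patients then no longer compares the groups that randomisation formed. If converted patients recover more slowly, dropping them flatters whichever arm has more conversions.

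The trial is meant to show superiority of end-to-side anastomosis on this endpoint. With no analysis set stated, the denominator could also be chosen after the results are seen. Conversion is not among the intraoperative items listed for collection in section 11, item 1(4), so a later check by arm is not secured.

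**Working it through.** **1. The plan's own figure.** Inputs from section 10, item 3: 90% vs 70%, alpha 5%, power 80%, 1:1, dropout 10%. Sidedness is not stated; two-sided is assumed. With unpooled variance:

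n = (0.9×0.1 + 0.7×0.3) × (1.960 + 0.842)² / 0.20² = 58.87, so 59 per arm. Then 59 × 1.1 = 64.9, so 65 per arm and 130 in total. The stated size reproduces and is not in question. After 10% loss, 65 × 0.9 = 58.5, taken as 58 per arm.

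**2. The timing statements side by side.** Section 11, item 1(2) is early, and section 11, item 2 matches it. Section 10, item 3 is late, and the Study Overview fits it: section 10 says the method is determined preoperatively, so an allocation during surgery is best read as its disclosure. The texts split about evenly and cannot all hold.

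**3. What exclusion does to an arm's rate.** Let p be recovery in all randomised patients, c the conversion rate and r recovery among converted patients. The rate after exclusion is (p − c·r)/(1 − c). The documents give neither c nor r; all values below are assumptions.

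**4. No true difference (p = 80% in both arms).** Exact binomial rejection rate of the two-sided 5% uncorrected chi-square, 58 per arm:

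| r | Conversion, arm A vs B | Rates after exclusion | False difference | False-positive rate |
|---|---|---|---|---|
| – | no exclusion | 80.0 vs 80.0 | 0 | 5.3% |
| 20% | 4% vs 2% | 82.5 vs 81.2 | 1.3 points | 5.6% |
| 20% | 6% vs 2% | 83.8 vs 81.2 | 2.6 points | 6.8% |
| 20% | 10% vs 2% | 86.7 vs 81.2 | 5.4 points | 12.7% |
| 40% | 6% vs 2% | 82.6 vs 80.8 | 1.7 points | 5.9% |
| 40% | 10% vs 2% | 84.4 vs 80.8 | 3.6 points | 8.4% |
| 60% | 10% vs 2% | 82.2 vs 80.4 | 1.8 points | 6.0% |

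Example, first 10% vs 2% row: (0.80 − 0.10×0.2)/0.90 = 0.867 and (0.80 − 0.02×0.2)/0.98 = 0.812. Of 65 patients, 10% is 6.5 and 2% is 1.3. With no exclusion the test's own rate ranges from 4.7% to 5.3% over 56 to 66 per arm, so the 4% vs 2% shift is negligible. Equal conversion with equal r gives a false difference of zero.

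**5. Planned difference (90% vs 70%, r = 20%, 58 per arm, more conversions in side-to-side).** No exclusion: 20 points, power 80%. Conversion 2% vs 4%: 91.4 vs 72.1, 19.3 points, power 80%. Conversion 2% vs 10%: 91.4 vs 75.6, 15.9 points, power 66%.

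**6. Late reveal.** A conversion before the allocation is opened cannot depend on knowledge of the arm, and the anastomosis has not yet been made. Leaving those patients out costs numbers but creates no false difference under the null. A conversion after the reveal could still be arm-related.

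**The case against.** The strongest reply is that the harm is inferred. Item 8 does not say that converted patients leave follow-up or analysis, and a reader who infers an express exclusion goes beyond the text. That stands: what can be shown is silence, with exclusion as the likely reading.

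A reader might also take the reveal time alone to settle whether there is bias. It does not. An early reveal creates bias only if conversion, or prognosis after it, differs by arm. The documents show neither, and section 11, item 1(2) says everything except the anastomosis is done identically. Nor does a late reveal protect against conversions after the arm is known.

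A third tempting reading is that an exclusion criterion in section 10, item 2 already covers converted patients: "Patients in whom laparoscopic surgery is not feasible due to a history of prior abdominal surgery or the severity of the disease". That is an eligibility rule about prior surgery and disease severity. Intraoperative conversion has its own entry in section 11, item 8, so the exclusion criterion adds no support.

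Finally, the sizes are hypothetical and mostly small. The 12.7% needs a fivefold imbalance together with only 20% recovery after conversion. This too stands, and it limits the weight of the point. It does not remove the two textual defects: no rule for counting converted patients, and incompatible reveal times.

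**Conclusion.** The concern holds as a gap plus a contradiction, and should be fixed. The plan has a withdrawal rule that can remove randomised patients, possibly with the arm known, and no statement keeps them in the primary denominator. Bias is possible, not demonstrated. On the assumed values it is negligible at 4% vs 2% conversion, modest at 6% vs 2%, and material only for an imbalance such as 10% vs 2% with poor recovery after conversion. The textual findings are firm for the text available for review; the magnitudes rest wholly on assumed conversion and recovery rates. The sample size of 130 is not in error.

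**What to change.** 1. Reconcile the Study Overview, section 10, item 3, and section 11, items 1(2) and 2, to one reveal moment.
2. Amend section 11, item 8 so that conversion after the allocation is opened does not end follow-up or remove the patient from analysis. The surgical decision itself is unaffected.
3. Define the primary set as all patients whose allocation was opened, analysed in the assigned arm with the same recovery criteria. Use the laparoscopic-completed set as a sensitivity analysis only. If the late reveal is kept, patients converted before opening fall outside the primary set by design; record their number.
4. Record and report conversions by arm and by timing relative to the reveal.
5. State whether the 130 counts enrolled patients or opened allocations, whether the 10% dropout includes conversions, and whether 90%/70% includes converted patients.

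**Cost.** Wording, plus day-7 follow-up of about 3 to 13 of 130 patients at an assumed 2% to 10% conversion (130 × 0.02 = 2.6; 130 × 0.10 = 13).

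The power cost depends on item 5 (exact chi-square power; the 65-per-arm figures assume no other loss):
- If 90%/70% already covers all randomised patients, 65 per arm gives 83%.
- If it was meant for non-converted patients only and no converted patient recovers, the rates become 0.9(1 − c) and 0.7(1 − c). Power at 65 per arm is then 79%, 73% or 64% at 2%, 5% or 10% conversion.
- Under a late reveal, with the 130 counting enrolled patients and conversions falling within the 10% dropout, 58 per arm keeps about 80%. If conversion were the only loss, 61 per arm (5% conversion) gives 81% and 58 (10%) gives 80%. Only if conversions come on top of the 10% does power fall: 65 × 0.95 × 0.9 leaves 55 per arm (77%), and 65 × 0.90 × 0.9 leaves 52 (74%).
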